8.0 Costs to Participants

- There are no costs to participants. The study will take approximately 1 hour initially (10 minutes consent, 15 minutes pre-test, 30 minutes education tool, 5 minutes post test). The one month follow survey will take approximately 30 minutes.
- For medical staff participants, surveys will take less than 5 minutes; post-intervention interviews will take approximately 30 minutes.

9.0 Consent Process

- The study coordinator will introduce the study and review the consent document either in person or over the phone. If providing consent over the phone, the staff member will read the consent to the participant (script provided). If they verbally agree, they will be directed to the link in their email for the study. The study consent document is then also embedded into the RedCAP baseline survey that will be on the iPad or computer. Participants will read through the consent and provide consent by entering their name and hitting a designated button. They then will be asked to do the same for the HIPAA consent. These consents will be recorded and the participant will be allowed to proceed to the baseline survey. If the participant has any questions about the study or consents, the site recruiter will be available in person or over the phone. Staff will have copies of the consent should the participant like to have a copy to take home; those doing at home can download a pdf of the consent to have a copy. The scripts for the staff person to explain this is included (App C). A telephone screening consent script is also provided.
- Participants will be able to decide to continue or discontinue at any time.
- All participants will be English speaking.

10.0 Off-Study Criteria

- Not applicable

11.0 Drugs and Devices

- Not applicable.

12.0 Multi-Site Research Study

- • Fox Chase Cancer Center serves as the primary site, with participating sites including sites Temple University Hospital, Thomas Jefferson University Hospital, and Hospital of the University of Pennsylvania. [name] serves as the PI at FCCC overseeing study recruitment at all coordinating sites. Each site will have their own IRB oversight and coordinating investigator as well as their own study documents (e-consent and protocol) to meet their institutions requirements. [name] and the study coordinator at FCCC will oversee the other sites regulatory by documenting the study team's Human Subjects training and expiration dates. They will also track all sites Continuing Reviews to ensure compliance across all 4 coordinating sites.
- [name] and the study coordinator at FCCC will also oversee protocol management by conducting monthly meetings and periodic review of each site's protocol. The study coordinator will conduct on-site visits monthly to review recruitment and study progress. All sites will participate in a monthly full team call to discuss updates and address any recruitment/implementation issues.
- Each site will be provided an Operations Manual that incorporates important protocol specific information to provide support onsite. Each member of the study staff will have 3 training sessions prior to their recruitment start date. We will also conduct periodic recruitment training to reinforce operations and protocol compliance.
- Data management will take place at FCCC via REDCap weekly by the Study Coordinator. The Study Coordinator will review quality and completeness of the data on a weekly basis and provide feedback to each site PI and recruitment staff.

13.0 Statistical Analysis

- **General analyses:** After screening for potential differences across sites on the key outcome variables, all data will be graphed and tabulated by group (i.e., **mychoice** vs. control) for review of distributional properties and anomalous values prior to the main analyses. Continuous and normally distributed variables will be summarized with means and standard deviations. All parameter estimates will be bound by 95% confidence intervals. Tests of significance will be based on adjustments for alpha to protect family-wise error rates at 5% using the method of Benjamini and Hochberg [40]. Data will be analyzed using an intent-to-treat (ITT) approach where subjects are analyzed according to their treatment assignment at randomization, regardless of level of participation or engagement. Because an ITT analysis is planned, we will evaluate models suitable for non-ignorable (missing not at random) data within a sensitivity analysis framework in order to determine the extent to which analysis conclusions depend on the assumptions being made about unobserved values. We will perform model-based analyses with direct maximum likelihood methods, including those for data missing not at random (MNAR) if necessary. We will screen for violations of assumptions for all statistical tests involved. All analyses for specific aims will be conducted using SAS 9.4.

- **H1 Analysis:** The principle endpoint will be 1-month follow-up, i.e., one month after completion of either the **mychoice** or control education. We will conduct a mixed-effect regression models for each repeatedly measured continuous outcome (i.e., self-efficacy and decisional conflict at post intervention and 1-month follow-up) on a dummy grouping variable (**mychoice**, as compared to Control), adjusting for baseline level of this outcome and covariates discovered to be unbalanced between the two groups, and moderators of interest. In these models, we will treat time as a categorical variable and examine the fixed effects for time, intervention group, and their interactions. We will specify the covariance structure within patients using an unstructured model to account for the in-patient correlation over time.

In addition, the dichotomous race (White vs. non-White) variable and the non-White-Treatment interaction will be entered in each regression model as predictors, to understand possible different effects of **mychoice** for non-White vs. White participants. A significant, positive regression coefficient of the non-White Treatment interaction indicates non-white participants' benefits more from the treatment than their White counterparts.

- **Power:** Power analyses were performed using G*Power 3.1, with 2-sided tests and an adjusted alpha level of .025 (= .05/2) for multiple group comparisons. We performed power analyses for comparisons on primary and secondary outcomes for Aim 1. Effect size (mean difference between groups divided by the pooled standard deviation) is a common measure for assessing the magnitude of a treatment effect on continuous outcomes. The number of participants needed for Aim 1 is selected to sufficiently power the detection of a difference between groups on the outcomes adjusting for covariates and moderators at 1-month follow-up.

To detect a moderate treatment effect size of 0.47 SD on either the self-efficacy and decisional conflict scales, our trial would need 88 patients per group, presuming alpha = .025 and beta = .20 (power = 80%). Of note, this effect size is comparable to prior studies (please cite some papers). Including a 20% adjustment for dropout and loss of degrees of freedom when adjusting for possible additional confounding variables, a total of 220 patients are needed. By using mixed-effects repeated measures regression analysis, our power is likely to be even higher. Therefore our estimated power provides a conservative lower-bound of the likely actual power of our sample size. Also, we will need an additional 50 patients to do exploratory analysis on potential differences in effect by recruitment type, bringing the total needed to 270.

- **H2 Analysis:** Descriptive statistics will be employed for the analysis of the quantitative feasibility and acceptability data. All qualitative data collected through the meeting notes and debriefing interviews will analyzed the Krueger method of analyzing narrative data will be used; familiarization, identifying a thematic framework indexing, charting, mapping and interpretation [80]. Recordings will be listened to and transcriptions read to become familiar with what participants said. A

thematic framework, based on the CFIR constructs will be developed to create categories and quotes will be indexed according to categories to reduce data. Major themes of the analysis will be reviewed across institutions. Recruitment logs will be reviewed and compared against study recruitment goals to determine potential barriers.

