In addition, we will assess barriers to implementation when introducing the tool in diverse cancer centers, each with different protocols and patient populations, to inform a future proposal. Using the Consolidated Framework for Implementation Science (CFIR), one of the predominant implementation science research frameworks, we will focus on five domains: intervention characteristics, outer settings, inner setting, characteristics of individuals (patients and providers), and process [28]. Implementation science is becoming an important component of intervention implementation and we aim to use this framework to ensure success.

- **Preliminary Data:** To address the issue of clinical trial participation, we developed **mychoice (IRB #14-811)** to target unique barriers of underrepresented populations and prepare them for a discussion about clinical trials with their providers [29-38]. The intervention was developed with stakeholder (both patients and providers) involvement and includes real life stories of cancer patients. The intervention, initially focused on African American cancer patients, was based on mixed-methods formative research including in-depth interviews (Phase I), a survey of African American cancer patients using perceptual mapping and vector modeling to guide the development of the communication messages within the intervention (Phase 2), and message and user testing of the mHealth tool with African American cancer patients who had never participated in clinical trials (Phase 3).

In Phase 1 we conducted in-depth interviews with 16 African American cancer patients. Investigators reviewed and developed themes/subthemes, which resulted in eight themes: knowledge, benefits, disadvantages, social support, decision influencers, provider beliefs, personal history, and value of clinical trials. Results from these interviews were used, along with a thorough literature

review, to inform the development of a quantitative survey that was used in Phase 2.

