- The email link will provide a contact name, phone number, and email should the participant have any questions or concerns. If they choose to come to the REC because they do not want to do the study at home, we will make an appointment with them to meet them at a designated day/time.
- The REDCap link will include pre/post-tests (Appendices D and E) for all patients, and the appropriate patient education materials based on randomization. (**Note:** Baseline surveys take approximately 15 minutes and post-test surveys take approximately 5 minutes, based on testing.) The pre and posttests as well as the consent form will be integrated into the materials through REDCap. All patients will then be contacted by telephone or email one month post consult by the research staff to conduct a follow-up survey (Appendix F – Treatment Arm; Appendix G – Control Arm). In some cases (i.e. at TUH) follow-ups will be done in person when the patient has returned for an appointment.
- The experimental condition will receive the *mychoice* mHealth Tool (Screen shots (<http://mychoice.sandstorm.notss.com>) of the tool are provided in Appendix G.) The entire tool is available at the URL. The control condition will receive the NCI material on clinical trials: Taking Part in Cancer Treatment Research Studies (<https://www.cancer.gov/publications/patient-education/CRS.pdf>). Both will be provided on the device through the RedCAP system. Participants in the experimental condition will receive a pair of ear buds (which they can keep) to listen to audio/video segments and will receive a printed version of the questions they identify as important to them.
- Patient participants will receive a total of \$50 compensation, provided as a \$25 gift card at initial testing and an additional \$25 upon follow-up survey. These will be provided in person if they choose to complete the study in person or via mail if they choose to complete the study at home. Recruiters and physicians interviewed about implementation will not receive compensation.

b) Inclusion and exclusion criteria

- **Eligibility criteria for participation in the RCT are:** 1. 18 years of age or over; 2. Active diagnosis of invasive cancer (any diagnoses); pre or post chemo/radiation/surgery; 3. Able to speak and read English
- **Exclusion:** Participated in a therapeutic trial in the past

c) Procedures involved in the human research

o Study Design: (Figure 2)

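### Site is screened against the outcomes with no stated consequence and is not prespecified in either primary model, at a modest cost in precision

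*Combined protocol and SAP*

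**What the plan says.** Site appears once in the statistical section, as a preliminary step: "After screening for potential differences across sites on the key outcome variables" (13.0, General analyses). No test, threshold or resulting action is given.

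The H1 Analysis paragraph in 13.0 then specifies one mixed model for each of the two primary outcomes, self-efficacy and decisional conflict. The named terms are:
- group, categorical time and group by time;
- the baseline value of the outcome;
- covariates found to be unbalanced between arms;
- moderators of interest;
- race, and race by treatment.

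The only covariance structure is within patients. Site is named neither as a fixed nor as a random effect. The Randomization item in 4.0 c) gives 1:1 REDCap assignment and mentions no stratification by site.

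The protocol also describes how the centres differ. Section 3.0 calls them "diverse cancer centers, each with different protocols and patient populations". Section 4.0 a) describes a resource-centre route and a common-area table at Fox Chase, and limits the other sites to physician referral and self-referral. The same section has the 1-month survey taken by telephone or email, with an exception: "i.e. at TUH) follow-ups will be done in person when the patient has returned for an appointment".

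**The concern.** The 1-month score is the principal endpoint. If scores at that point differ by centre for reasons that baseline score and race do not capture, the difference sits in the residual of a model without site. Because assignment is not stated to be stratified by site, it also reaches the treatment estimate through chance differences in how the arms split within sites. These are one loss seen from two sides, a wider standard error, and should not be counted twice.

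The second issue is prespecification. A screen on the outcomes is a poor basis for choosing the primary model. It may miss a modest site difference, and when it finds one the plan states no action. The form of the primary model is then settled after outcome data have been seen.

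**Working it through.** **Inputs from section 13.0, Power.** Test: "with 2-sided tests and an adjusted alpha level of .025 (= .05/2"). Error rates: "presuming alpha = .025 and beta = .20 (power = 80"%). Effect: "To detect a moderate treatment effect size of 0.47 SD". Size: "our trial would need 88 patients per group". Inflation: "Including a 20% adjustment for dropout and loss of degrees of freedom", giving 220, then 50 more for 270. Section 12.0 counts four sites. Section 2.0 speaks of three centres; four is used here.

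**Assumed.** The share s of 1-month variance lying between sites after baseline and race adjustment is not given. Values from 1% to 10% are tried.

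**Step 1. The plan's own figure.** Normal approximation: n = 2(2.241 + 0.842)² / 0.47² = 86.1, so 87 per group. The exact noncentral-t calculation gives 88 (power 80.3%). Then 176 / 0.80 = 220. The stated sizes reproduce and do not depend on site.

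**Step 2. Loss from omitting site.** Taking the total SD as 1, a site term reduces the residual SD to √(1 − s). Without it the standard error is larger by the factor 1/√(1 − s). Power is by noncentral t at 88 per group.

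| s | SE larger by | Power, no site term | Power, site term |
|---|---|---|---|
| 1% | 0.5% | 80.3% | 80.8% |
| 2% | 1.0% | 80.3% | 81.2% |
| 5% | 2.6% | 80.3% | 82.5% |
| 10% | 5.4% | 80.3% | 84.6% |

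The last column does not yet charge for estimating the site effects.

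**Step 3. Charge for the site terms.** Four sites cost 3 degrees of freedom, worth about 3 patients of information under unstratified assignment. With 270 × 0.80 = 216 analysed, the gross gain is 216/(1 − s) − 216 and the net gain is 213/(1 − s) − 216.

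| s | Gross gain (patients) | Net gain (patients) | Net SE penalty for omission, √[213 / (216(1 − s))] − 1 |
|---|---|---|---|
| 2% | 4.4 | 1.3 | 0.3% |
| 5% | 11.4 | 8.2 | 1.9% |
| 10% | 24.0 | 20.7 | 4.7% |

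Break-even is at s = 3/216 = 1.4%. If sites do not differ at all, including site enlarges the standard error by √(216/213) − 1 = 0.7%.

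**Step 4. What the screen would find.** The plan names no test, so a 5% F test across four sites on 216 patients is assumed, with noncentrality 216s/(1 − s) on 3 and 212 degrees of freedom. Its power is 39% at s = 2%, 81% at 5% and 99% at 10%. A small site effect is usually missed; a larger one is usually found, with no stated consequence.

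**Step 5. Type I error.** A simple two-group comparison was simulated with 10,000 runs per setting, unstratified 1:1 assignment, nominal 2.5%, assumed site sizes of 115, 100, 28 and 27, and site shares of 0, 5% and 10%. Rejection under the null was 2.3% to 2.6%, with or without a site term. There is no inflation.

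**The case against.** **Site is not excluded.** A reader might infer that site stays out of the models whatever the screen shows. The text does not say so. Site could enter as a covariate found unbalanced between arms, or as a moderator, and the Power paragraph allows for further confounders. This stands. What remains is that both routes depend on the data, and that the covariate route is triggered by arm imbalance, not by the site screen.

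**Site differences are not shown.** A reader might infer that variation between sites in the outcomes is known. No section reports any. The description of the centres in 3.0 comes from a sentence about barriers to implementation. The in-person follow-up is confined to some cases, so survey mode also varies within that site, and a site term does not remove that part. These facts make a difference plausible and no more.

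**Other terms absorb some of it.** Baseline score and race are already in the models and take up any site differences that run through them. This stands, and is why s is defined as what is left.

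**Power is ample.** At 216 analysed (108 per group) power for 0.47 SD is already 88.3% without site. Before the full information charge it would be 89.0%, 90.0% or 91.6% with site at 2%, 5% or 10%. This stands and keeps the severity low.

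**The form of adjustment is partly preference.** A random site effect, pooled small sites, or omitting site by time are all defensible. The case is for choosing one in advance.

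**Conclusion.** The point holds as a low-severity improvement in precision and prespecification. The outcome screen leads nowhere in the plan, and the treatment of site in the two primary models is left open until data are seen.

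The size rests on an assumed residual site share. At 2%, 5% or 10%, omission enlarges the treatment standard error by 1.0%, 2.6% or 5.4% gross, equivalent to 4, 11 or 24 of 216 analysed patients, or about 1, 8 or 21 after paying for the site terms. At 2% the net gain is close to nil, and below about 1.4% there is none.

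A reader might go further and infer bias, an inflated false-positive rate or an inadequate sample size. The documents and the calculations support none of these. Site sizes are only partly fixed, since section 4.0 a) gives one combined remainder for the two smaller centres and two of its ranges carry strike-through marks. The simulated sizes are therefore illustrative.

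**What to change.** In section 13.0, H1 Analysis, state that site enters both primary models as a fixed effect regardless of any site comparison. Add a rule, set before outcome data are seen, for pooling the two smallest sites if their numbers are too low to estimate separately. Turn the opening screen into a descriptive table of outcomes by site that plays no part in model choice. Site by time is optional; it would raise the cost from 3 to 6 degrees of freedom.

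The cost is one or two sentences, no new data beyond the recruiting site, about 3 degrees of freedom, and a standard error about 0.7% larger if the sites turn out not to differ. The Power paragraph already allows for degrees of freedom lost to adjustment, so the sample size need not change.

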4.0 Study Design

a) Recruitment methods

- We will recruit a total of 270 patients (~~100-130~~ at FCCC via the medical oncology, radiation oncology, and surgery units and 100 at TUHS via the cancer center). The remaining ~~40-70~~ patients will be recruited at Thomas Jefferson University Hospital and The University of Pennsylvania We anticipate that approximately 20% of the participant pool will be non-white which should provide sufficient number to perform sub-analyses of effects. We will monitor this during recruitment, however, and if we find that we are not reaching this number of non-white participants, we will change the protocol to focus on recruiting only non-white participants.
- There are three ways that patients will be recruited for the study at FCCC. This is shown in Figure 1.

- (1) First, at FCCC, [name] will collaborate with FCCC oncologists to identify patients who might be offered a clinical trial but who have not participated in a clinical trial previously. A patient information card and a flyer have been developed for oncologists to provide to patients (see

Appendices A and B). Oncologists will suggest the study to patients at regular visits and be instructed to either go to the Resource and Education Center at Fox Chase, or find a study representative in the waiting area at a table who is wearing a mychoice pin. Mychoice study staff will be in the waiting areas of participating oncologists on days/times that are busiest. If staff are not available that day, they can go to the REC. If the patient approaches a study staff, they will meet the patient in a designated private space, consent them, and give them the option of doing the study then on either a provided iPad or go to the REC to do the study on a computer.

- (2) Study staff will also be available in the common areas of FCCC at a table. Patients can come up to the table and ask about the study. We will also have a small “wheel” that is a game that patients can play to win small prizes (candy, umbrella, \$5 gift cards). All patients who come up to the table can play and win a small prize; there is no requirement to enroll in the study to play. If they are interested in the study, we will provide an information card and answer any questions they have. They can then complete consent and do the study then (as above) or have the option to complete the study at home.

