- (3) Another way for patients to participate is through a referral by REC staff. When patients go to the REC, staff will provide information to the patients about the study. If they are interested, REC staff will go through the above steps to consent a patient and provide them an iPad or computer to complete the study.
- (3) The last way for patients to participate will be by self-referral. Cards and posters will be available throughout the waiting areas. On this card are the study email and phone number. Patients could use these to contact study staff who will explain the study and verbally consent people over the phone and then provide the option to come to do the study at home or at the REC. Because this consent is occurring over the phone, staff will use a script (provided) to explain the study and screen for eligibility. A waiver of document of consent has been provided to assist with this process. After they have verbally been consented for the study, they will be sent a link to the study through the RedCAP system and provided information on how to complete the study. They will be directed to review the study consent and indicate their willingness to participate by entering their name as an e-signature. They then will be asked to do the same with the HIPAA waiver. Once they agree, they will be directed to the baseline survey.
- Patients recruited at TUH, Jefferson, and HUP will follow the same recruitment strategies, but will only be recruited by Physician Referral and Self-Referral. There are no REC staff at these institutions, so recruitment strategies will rely solely on study staff and physicians. Study staff will be in the waiting rooms prepared for any referrals during busy clinic days.

[figure not shown]
- All study materials, including the pre and posttest and the patient education materials, are programmed in REDCap. If completing the study in person, once the patient agrees to be in the study and is set up in the RedCAP system, study staff will explain this process and have them sign in the REDCap system to indicate they agree to participate (script for staff to follow in Appendix C) and to the HIPAA waiver. Study assignment will be random and programmed into the system

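### Covariates in the primary models are chosen by chance imbalance rather than prognostic value, and site is screened on the outcomes but is not a stated model term

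*Combined protocol and SAP*

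**What the plan says.** The H1 Analysis paragraph of section 13.0 covers both primary outcomes, self-efficacy and decisional conflict. Each is regressed "on a dummy grouping variable" in a mixed model with categorical time, group and group-by-time, and an unstructured within-patient covariance. The adjustment is described as "adjusting for baseline level of this outcome and covariates discovered to be unbalanced between the two groups, and moderators of interest". The next paragraph adds race (White versus non-White) and says that "the non-White-Treatment interaction will be entered in each regression model as predictors". Race is the only moderator named for these models.

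Site appears once in the analysis section, as a preliminary step: "After screening for potential differences across sites on the key outcome variables". What follows from that screen is not stated, and site is neither a fixed nor a random effect in the model description. Section 12.0 lists four centres. Section 4.0 describes 1:1 randomisation and states no stratification by site.

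The Power paragraph gives 88 per group for 0.47 SD at two-sided alpha .025 and 80% power, then reaches 220 with this allowance: "Including a 20% adjustment for dropout and loss of degrees of freedom when adjusting for possible additional confounding variables". It adds 50 patients for exploratory work on recruitment type, giving 270.

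**The concern.** Under randomisation, a difference between arms in a baseline covariate is chance. It does not show that the covariate predicts the outcome, and prediction is what determines whether adjustment buys precision. A 5% imbalance screen would admit a truly prognostic covariate only about one time in twenty. The plan also sets no cut-off and no candidate list, so the covariate set is decided after data are seen.

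Site is a natural candidate for the model, because section 4.0 shows centres differing in ways that could relate to the outcome. At the three centres other than Fox Chase, patients follow the same strategies "but will only be recruited by Physician Referral and Self-Referral". Follow-up is by telephone or email, except that "In some cases (i.e. at TUH) follow-ups will be done in person when the patient has returned for an appointment".

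The race interaction raises a related question about what the model estimates. With dummy coding and White as reference, the treatment coefficient is the effect in White patients. Hypotheses H1 and H2 in section 2.0 concern all patients, and the plan does not say which contrast tests them.

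At stake are precision, an analysis model fixed in advance, and a clear overall effect. Bias in the randomised comparison is not at issue.

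**Working it through.** **Inputs from the documents.** Two-sided alpha .025; effect 0.47 SD; 88 per group; 20% allowance; 270 enrolled (section 13.0). Four sites (section 12.0). On race, section 4.0 says "We anticipate that approximately 20% of the participant pool will be non-white".

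**Reproducing the plan's figures.** By noncentral t with df = 2n − 2 and noncentrality 0.47 × √(n/2), n = 88 gives power .803, so 88 is right. 2 × 88 / 0.80 = 220 and 220 + 50 = 270.

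**Reference powers.**
- 270 × 0.80 / 2 = 108 per arm: .883.
- 108 per arm with baseline-outcome correlation r = .5, effect 0.47 / √(1 − .25) = 0.543: .958.
- White patients only, 0.80 × 88 ≈ 70 per arm: .696.

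**How often imbalance appears by chance.** Assume independent items screened at 5%. The probability of at least one flag is 1 − .95^8 = 34% for the 8 demographic items in Table 1. It is 1 − .95^20 = 64% for 20 items (8 demographic, 6 cancer and trial experience, 5 technology, 1 literacy).

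**Simulation.** 20,000 trials per cell; linear model at 1 month with baseline, race (20% non-white) and race-by-treatment; effect averaged over race. Assumptions not in the documents:
- six candidate covariates screened by t-test at 5%, two of them prognostic;
- those two explain 0, 5 or 10% of the variance left after baseline, and site explains 0 or 2%;
- site shares of 115/100/27.5/27.5 out of 270.

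The fixed set is site (3 terms) plus the two covariates. Power is shown as no extra adjustment / imbalance rule / fixed set:

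| Covariate R², site R² | 88 per arm, r = 0 | 108 per arm, r = 0 | 88 per arm, r = .5 | 108 per arm, r = .5 |
|---|---|---|---|---|
| 0, 0 | .796/.792/.785 | .879/.876/.873 | .905/.902/.895 | .957/.955/.952 |
| .05, 0 | .792/.788/.803 | .876/.875/.885 | .902/.900/.911 | .956/.955/.960 |
| .10, 0 | .798/.800/.832 | .887/.887/.909 | .902/.902/.925 | .953/.955/.966 |
| .05, .02 | .798/.798/.820 | .881/.881/.897 | .905/.904/.917 | .956/.955/.964 |
| .10, .02 | .796/.798/.839 | .878/.881/.910 | .905/.905/.934 | .956/.956/.974 |

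The imbalance rule is never more than 0.3 points above no extra adjustment. Where the added terms are prognostic, fixed set minus rule, by subtraction, is:
- 88 per arm, r = 0: 1.5 to 4.1 points;
- 108 per arm, r = 0: 1.0 to 2.9 points;
- 88 per arm, r = .5: 1.1 to 2.9 points;
- 108 per arm, r = .5: 0.5 to 1.8 points.

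In the first row the fixed set is 0.3 to 0.7 points below the rule.

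**Type I error** (nominal .025, simulation error .001; covariate R² .10, site R² .02): rule .022-.024, fixed set .025-.027.

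**Discretion, as an illustration only.** Suppose an analyst takes the most favourable of eight readings: no covariates, or imbalance cut-offs of .05, .10 or .20, each with or without site. Type I error then rises from .025 to .037. Nothing in the plan says this would be done.

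**Which coefficient is read.** Without added covariates, the White-reference treatment coefficient has power .692-.697 against .793-.796 for the race-averaged contrast at 88 per arm, r = 0. At 108 per arm, r = .5, the figures are .899-.903 against .955-.958.

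**The case against.** The case against is mainly about size. Applied mechanically, the rule is valid: no bias, and type I error slightly below nominal. With no stratification by site stated, leaving site out is not an error. The model already fixes baseline outcome and enrolment is 270, so 108 per arm with an informative baseline is arguably the most realistic setting. There the gain is at most about 2 points on power already near 95.5%. The explained variances are assumed, and nothing in the documents shows that education or health literacy predicts these outcomes beyond baseline. All of this stands and limits the point to a modest improvement.

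Two further arguments carry less weight. The plan does explore recruitment type, with 50 patients added for it, but that exploratory analysis does not put site in the primary models. A site term is also only a rough proxy for follow-up mode, since in-person follow-up occurs in some cases only; that limits what site can explain but does not favour the imbalance rule.

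The race-contrast question is separate from covariate selection, and the plan never says that the White-reference coefficient is the overall test. That is fair. It still belongs here, because the interaction enters every primary model and the same sentence of the SAP has to settle it.

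**Conclusion.** The concern holds as something that should be changed; it is not a threat to validity. The plan states a selection rule that recovers essentially no precision and leaves the covariate set open until data are seen. It also screens site on the outcomes without saying what follows. A fixed prognostic set with site does better by about 0.5 to 4 points of power if two covariates explain 5-10% of the residual variance and site 0-2%. It does slightly worse if they explain nothing. The simulation uses a single time point in place of the full repeated-measures model, so the figures are indicative. The larger effect comes from how the overall result is read: roughly 10 points at 88 per arm with an uninformative baseline, and roughly 6 at 108 per arm with r = .5, if the White-reference coefficient were taken as the overall effect.

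**What to change.** Use one adjustment set for both primary models: baseline level of the outcome, site as a fixed effect, race and its treatment interaction, and two or three named baseline covariates. The team should name these before unblinded analysis, on expected prognostic value. Education and health literacy, both collected at baseline under Table 1, are examples. State that neither the imbalance check nor the site screen selects the model, and that any other adjustment is a sensitivity analysis.

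State also that the overall effect on each outcome is the 1-month mychoice-control contrast averaged over race in the sample proportions, or comes from the same model without the interaction.

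The cost is SAP wording; the named covariates are already collected. If site and the two covariates explain nothing, the five terms cost about 1 point of power against no extra adjustment at 88 per arm (79.6% to 78.5%) and 0.5 to 0.6 points at 108. Almost all of that comes from chance correlation of the added terms with group; lost degrees of freedom alone cost .0002 (.8034 to .8032). No separate reserve exists for it, since 176 / 0.80 = 220 means that 20% dropout alone would use the whole allowance. The sample size need not change.
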